5.2 Chemotherapy details

5.2.1 Cisplatin

- Chemistry: Cisplatin (cis-diamminedichloroplatinum II) has the empiric formula $\text{H}_6\text{Cl}_2\text{N}_2\text{Pt}$. It is a planar inorganic compound with a molecular weight of 300; soluble in water at a concentration of 1 mg/ml. The (II) nomenclature denotes the (active) valence state of the platinum. The interatomic distance of the chlorides is 3.3 Å which is different from the 5-7 Å interatomic distance of the classic alkylating agents. Only the cis-isomer is therapeutically active.
- Mechanism of Action: Primarily causes inhibition of DNA synthesis, and to a lesser degree inhibition of RNA and protein. It has not been shown to be cell cycle specific.
- Human Pharmacology: Highest concentrations were found in kidney, liver, and spleen; lowest concentrations were found in the brain. Plasma contained less than 10% of dose at 1 hour and the peak urinary excretion was 22-32% in 48 hours. It has a biphasic mode half-life, the initial phase of 25-49 minutes, and the secondary, 58-73 hours. The drug was 79% protein bound with intracellular leukocyte levels 6.1% of plasma levels.
- Side Effects: Impairment of renal function, myelosuppression, high-frequency hearing loss, nausea and vomiting.

5.2.1 5-Fluorouracil

- Chemistry: 5-fluorouracil has the empiric formula $\text{C}_4\text{H}_3\text{FN}_2\text{O}_2$. It is a pyrimidine analog and blocks thymidylate synthetase conversion of deoxyuridylic acid to thymidylic acid.
- Mechanism of action: 5-fluorouracil (5-FU) is a pyrimidine analog antimetabolite that interferes with DNA and RNA synthesis; after activation, F-UMP (an active metabolite) is incorporated into RNA to replace uracil and inhibit cell growth; the active metabolite F-dUMP, inhibits thymidylate synthetase, depleting thymidine triphosphate (a necessary component of DNA synthesis).
- Human pharmacology: 5-FU Penetrates extracellular fluid, CSF, and third space fluids (eg, pleural effusions and ascitic fluid), marrow, intestinal mucosa, liver and other tissues. It

exhibits primarily Hepatic metabolism (90%) via a dehydrogenase enzyme; FU must be metabolized to be active metabolites, 5-fluorouridine monophosphate (F-UMP) and 5-5-fluoro-2'-deoxyuridine-5'-O-monophosphate (F-dUMP). Half life elimination is 16 minutes (range: 8-20 minutes); two metabolites, F-dUMP and F-UMP, have prolonged half-lives depending on the type of tissue. 5-FU is excreted in lung (as expired CO₂) and urine (7% to 20% as unchanged drug within 6 hours; also as metabolites within 9-10 hours).

- **Side effects:** Primary side effects include nausea, diarrhea, and maculopapular rash. Cardiovascular and hematologic side effects are rare.

6.0 TRIAL PROCEDURES*

Figure 2-

[figure not shown]

Table 1-

Trial Period:	Screening Phase	On-Treatment Monitoring Visit							Post-Treatment
		Week 1	Week 2	Week 3	Week 4	Week 5	Week 6		
	Study Screening								Survival Follow-Up
Scheduling Window (Days):	4 weeks to 0 days prior to beginning of CRT	Fraction 1-5 of CRT	Fraction 6-10 of CRT	Fraction 11-15 of CRT	Fraction 16-20 of CRT	Fraction 20-25 of CRT	Fraction 26-29 of CRT if applicable		12+/-4 wks after end of CRT and then per SOC FU algorithm (Table 2)
Administrative Procedures									
Informed Consent	X								
Medical History	X								
Survival Status									X ^c
Clinical Procedures/Assessments									
Directed Physical Examination	X ^a	X	X	X	X	X	X		X
Weight	X	X	X	X	X	X	X		X
ECOG Performance Status	X	X	X	X	X	X	X		X
Radiation CT-Simulation	X ^b	X ^b	X ^b	X ^b	X ^b	X ^b	X ^b		
Physician-assessed CTCAE v4		X	X	X	X	X	X		X ^c
Patient-reported PRO-CTCAE		X	X	X	X	X	X		X
Chemoradiation Treatment		X	X	X	X	X	X		
Laboratory/Imaging/Assessments									
Pregnancy Test – Urine or Serum HCG	X								
CBC with Differential including ANC and ALC	X	X	X	X	X	X	X		X
Quality of Life Questionnaires	X ^d								X ^d
PET/CT + contrast or CT chest/abdomen/pelvis with contrast	X								X
Anoscopy or Flexible Sigmoidoscopy	X								X ^e

Trial Period:	Screening Phase	On-Treatment Monitoring Visit						Post-Treatment
		Week 1	Week 2	Week 3	Week 4	Week 5	Week 6	
Scheduling Window (Days):	Study Screening 4 weeks to 0 days prior to beginning of CRT	Fraction 1-5 of CRT	Fraction 6-10 of CRT	Fraction 11-15 of CRT	Fraction 16-20 of CRT	Fraction 20-25 of CRT	Fraction 26-29 of CRT if applicable	Survival Follow-Up 12+/-4 wks after end of CRT and then per SOC FU algorithm (Table 2)

*All are standard-of-care tests/procedures/charges.

- a. The first physical examination during the screening period will be a full examination, all subsequent examinations will be directed
- b. Patients will be simulated followed approximately one week or more prior to starting radiation therapy. Initial CT simulation is required for treatment planning, and at least one verification CT simulation is required during treatment, but verification CT simulations can be done as often as weekly at the discretion of the treating physician.
- c. In lieu of an in person visit, all subsequent follow ups after the first follow up can be conducted over the phone. In these instances a directed physical examination will not be required and appropriate outside imaging scans must be utilized to assess response.
- d. EQ-5D, EORTC QLQ -C30, Perceived Stress Scale, FSFI (women) and IIEF (men).
- e. Baseline and 12 week follow up endoscopy must be performed at MD Anderson. Schedule of follow up endoscopies after the 12 week follow up will be decided by the managing team based on findings.

Figure 2 and Table 1 above summarize the trial procedures to be performed at each visit. Individual trial procedures are described in detail below. Patients are strongly encouraged to maintain follow up at MD Anderson. If unable to do so due to unexpected logistical or financial consideration, patients will be advised to maintain the follow up schedule with an outside oncologist as per the current standard of care- and have all imaging and clinical documentation forwarded to MD Anderson. Additional history and/or QOL instruments will be emailed via REDCap or collected over the phone as needed by the study team. The first follow up study visit as well as all required tests at 12+/-4 weeks after completion of CRT will be required to be at MD Anderson.

6.1 Pretreatment Procedures

- 6.1.1 Patients will be screened for eligibility from 30 days prior to the start of CRT to the day of the start of CRT (provided that consents are signed before radiation treatment starts) (see section 4.0). A medical history will be obtained by the investigator or qualified designee. Medical history will include all active conditions, and any condition diagnosed that are considered to be clinically significant by the Investigator. Details regarding the disease for which the subject has enrolled in this study will be recorded separately and not listed as medical history.
- 6.1.2 The treating physician or qualified designee will perform a full physical examination at the first pretreatment evaluation including documentation of the primary anal lesion size and distance from the anal verge up to 30 days prior to registration.
- 6.1.3 The treating physician or qualified designee will record weight at the first pretreatment evaluation, weekly clinic visits and during follow-up).
- 6.1.4 The investigator or qualified designee will assess performance status using the Eastern Cooperative Oncology Group (ECOG) Performance Scale at screening and at every subsequent study visit.
- 6.1.5 Informed consent: the investigator must obtain document informed consent from each potential subject prior to participating in a clinical trial (Appendix).
- 6.1.6 MD Anderson pathology review of the biopsy specimen (if not performed at this institution) for histologic confirmation of squamous cell carcinoma. Human Papilloma Virus (HPV) determination will be noted from the biopsy specimen if available.
- 6.1.7 Endoscopic examination of the anal canal on either sigmoidoscopy or rigid proctoscopy will be completed prior to initiation of CRT and 7 days after initiation of CRT (although endoscopic examination prior to the start of CRT is strongly encouraged).
- 6.1.8 Contrast-enhanced PET/CT scan or CT scan of the chest, abdomen and pelvis with contrast up to 60 days prior to initiation of CRT unless the patient has a documented contrast allergy.
- 6.1.9 Baseline labs will be obtained, including complete blood count (CBC: hemoglobin, hematocrit, WBC with differential blood cell counts (neutrophils, bands, lymphocytes, monocytes, eosinophils, basophils) and platelets. Women of child-bearing potential require a urine pregnancy test (beta-hCG) prior to simulation.

6.1.10 Patients will report baseline symptoms and quality of life with the following instruments as outlined below. Questionnaires will be administered electronically and paper copies of the questionnaires will be available if necessary.

- The EQ-5D-5L
- The EORTC QLQ-C30 will be utilized to report GI-specific quality of life
- The Perceived Stress Scale
- For female patients:
Female Sexual Function Index (FSFI)- 19 question survey validated in cancer survivors.
- For male patients:
Individual Items of International Index of Erectile Function Questionnaire (IIEF).

6.2 On-treatment Procedures

6.2.1 Radiation treatment will be preceded approximately 1 week or more by radiation treatment planning simulation consisting of a non-contrast CT scan in the treatment position. At least one verification CT scan in the treatment position is required after the initiation of treatment. The treating radiation oncologist should review the internal anatomy on the verification scan with respect to the initial treatment planning scan and review the target coverage as well as doses to normal organs on the verifications scan with respect to the initial treatment plan. Adaptive plans can be generated if deemed clinically necessary by the treating radiation oncologist. Additional verification scans can be obtained up to weekly if deemed necessary by the treating radiation oncologist. See section 5.1 for further details on radiation treatment.

6.2.2 Chemoradiation will be administered using doses of both radiation and chemotherapy consistent with the current institutional standard of care (further details provided in sections 5.1 and 5.2).

6.2.3 On-treatment evaluation consists of weekly clinic visits with the treating radiation oncologist who will assign CTCAE v4 toxicity grades of hematologic, gastrointestinal, genitourinary and dermatologic side effects GI: nausea, vomiting, diarrhea, constipation, anal pain, proctitis, and fecal incontinence; GU: urinary frequency, urinary urgency, urinary tract pain, urinary incontinence, vaginal pain (women only), and perineal pain; Dermatological: radiation dermatitis). Patients will also report toxicity using the PRO-CTCAE. Weekly blood work will be monitored by both the treating medical and radiation oncologists including: complete blood count (CBC: hemoglobin, hematocrit, WBC with differential blood cell counts (neutrophils, bands, lymphocytes, monocytes, eosinophils, basophils, platelets, and febrile neutropenia). A focused physical examination, weight and ECOG performance status will be assessed at each weekly visit.

6.2.4 For all patients enrolled on study, charges and TDABC data will be collected from the date of initial consultation until the 12 week follow up. Data will capture all visits, treatments, procedures, interventions, emergency room visits and hospital admissions within the MDACC system. Total cost of care will be calculated for each enrolled patient. Total professional and technical charges will also be calculated for each enrolled patient with the assistance of the billing department.

6.3 Post-treatment Follow-up Procedures

- 6.3.1 The treating physician or qualified designee will perform a focused physical examination at the first follow-up evaluation including documentation of clinical response to treatment (complete clinical response, partial clinical response/residual disease, or progressive disease). .
- 6.3.2 The treating physician or qualified designee will record weight at the first follow-up evaluation.
- 6.3.3 The investigator or qualified designee will assess performance status using the Eastern Cooperative Oncology Group (ECOG) Performance Scale at the first follow-up evaluation.
- 6.3.4 Endoscopic examination of the anal canal on either anoscopy, sigmoidoscopy or rigid proctoscopy at the time of the first follow-up evaluation (12+/-4 weeks from completion of CRT).
- 6.3.5 Contrast-enhanced CT scan of the chest, abdomen and pelvis with contrast at the time of the first follow-up evaluation (12+/-4 weeks from completion of CRT) unless the patient has a documented contrast allergy or inadequate renal function. The CT will be read by a staff radiologist as per the current standard of care. Dimensions of any residual tumor should be recorded where applicable.
- 6.3.6 Labs will be obtained at the first follow-up evaluation including complete blood count (CBC: hemoglobin, hematocrit, WBC with differential blood cell counts (neutrophils, bands, lymphocytes, monocytes, eosinophils, basophils) and platelets.
- 6.3.7 At the first follow-up evaluation, patients will report symptoms and quality of life with the following instruments as outlined below. Questionnaires will be administered electronically and paper copies of the questionnaires will be available if necessary.
 - The PRO-CTCAE
 - The EQ-5D.
 - The EORTC QLQ-C30 will be utilized to report GI-specific quality of life
 - The Perceived Stress Scale
 - For female patients:
Female Sexual Function Index (FSFI)- 19 question survey validated in cancer survivors.
 - For male patients:
Individual Items of International Index of Erectile Function Questionnaire (IIEF).
- 6.3.8 Patients should be followed every 12+/-4 weeks for the first two years per the current standard of care with physical exam, labs, imaging and endoscopy at the discretion of the treating physicians (See Table 2). Only the first follow-up visit will be required on study. However, the questionnaires mentioned in 6.3.7 above will be sent via email using REDCap at 6 month intervals for voluntary participation for 24 months after treatment completion. Patients returning for follow up at MD Anderson will have their medical records queried for response rate, local progression free survival, distant metastasis-free survival and overall survival at each subsequent visit for 48 months after treatment completion.

Table 2

Time from Completion of Treatment	Evaluation	Team Providing Clinical Follow-up
3 months	PE, CT, scope	MO, XRT, CRS
6 months	PE, scope	MO + CRS*
9 months	PE	XRT
12 months	PE, CT, scope	MO + CRS
15 months	PE	XRT
18 months	PE, CT (CT not needed if <T3 or <N2)	MO
21 months	PE	XRT
24 months	PE, CT, scope	MO + CRS
30 months	PE	XRT
36 months	PE, CT, scope	MO
42 months	PE	XRT
48 months	PE, CT	MO
>48 months		Survivorship or discharge to PCP for routine care

*initial visits with CRS for proctoscopy until complete response or disease persistence is established.

PE = physical exam, CT = computed tomography, MO = medical oncology, XRT = radiation oncology, CRS = colorectal surgery, PCP = primary care physician.

6.4 Administrative/Other Procedures

6.4.1 Subject Withdrawal/Discontinuation Criteria: Subjects may withdraw consent at any time for any reason or be dropped from the trial at the discretion of the investigator should any untoward effect occur. In addition, a subject may be withdrawn by the investigator if enrollment onto the trial is inappropriate, if the trial plan is violated, or for administrative and/or other safety reasons.

A subject must be discontinued from the trial for any of the following reasons:

- The subject or legal withdraws consent.
- Inter-current illness that prevents further monitoring.
- Investigator's decision to withdraw the subject.
- The subject has a confirmed positive serum pregnancy test.
- Noncompliance with trial treatment or procedure requirements.
- The subject is lost to follow-up.

Additional subjects may be enrolled on an as-needed basis to substitute for patient's removed prior to the first follow up visit after chemoradiation.

6.4.2 Adverse Event (AE) Monitoring: The investigator or qualified designee will assess each subject to evaluate for potential new or worsening AEs as specified in the Trial Flow Chart and more frequently if clinically indicated. Adverse experiences will be graded and recorded throughout the study and during the follow-up period. Toxicities will be characterized regarding

seriousness, causality, grading, and action taken with regard to trial treatment. Grading will be determined utilizing CTCAE v. 4.0.

6.4.3 Trial Database: All data on trial including toxicities, demographics, medical history, and treatment response will be entered into a trial-specific REDCap database.

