7.3 Evaluability

To be evaluable for toxicity, patients must have at least one weekly assessments of adverse events (CTCAEv4).

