7.4 Statistical Analysis Plan

7.4.1 Primary Clinical Endpoint: *To assess physician-reported acute grade 3 or greater gastrointestinal, genitourinary and hematologic toxicities at 12 weeks post-treatment for patients treated with linear energy transfer (LET)-optimized, intensity-modulated proton therapy (IMPT) and compare to contemporary controls treated with VMAT to determine the feasibility of this outcome for a future randomized trial.*

- At baseline, weekly during treatment, and at the 12 week post-treatment follow up appointment, the treating physician will document physician-assessed acute hematologic, gastrointestinal, genitourinary, dermatologic and other toxicities according to the Common Toxicity Criteria for Adverse Events v-4 (CTCAE v4).
- For each cumulative physician-reported toxicity (hematologic, gastrointestinal, genitourinary, dermatologic and other) at 12-weeks post-treatment, we will tabulate results by type, grade, and attribution and compare with contemporary controls treated with standard of care VMAT-based chemoradiation with 5FU and cisplatin for non-metastatic anal squamous cell carcinoma manually and individually matched for (in order): T-stage, radiation dose, age and gender. We will compare toxicity rates using a McNemar's chi-squared test for paired proportions.
- A separate PA protocol will be submitted to retrospectively review the data from these contemporary controls.
- Subset analyses will be carried out to evaluate the effect of other variables that may also impact toxicity in addition to radiation modality (IMPT vs VMAT).

On RTOG 0529, patients treated with dose-painted IMRT-based concurrent CRT for anal cancer had reported worst overall G3 or greater toxicity rates of 83%. GU/GI G3 or greater toxicity rates were 21%, dermatologic G3 or greater toxicity rates were 23% and hematologic G3 or greater toxicity rates were 58% ⁴.

To ensure an LET-optimized IMPT-based CRT approach is not overly toxic, we will monitor physician-assessed toxicity using the Bayesian optimal phase 2 (BOP2) design ²⁸. Specifically, let n denote the interim sample size and N denote the maximum sample size. Let p_{tox} denote the probability of G4 or greater toxicity and define the null hypothesis $H_0: p_{tox} > 0.5$, representing that the treatment is too toxic. We will stop enrolling patients and inspect the safety data for possible trial termination if

$$Pr(p_{tox} \leq 0.5 | data) < \lambda \left(\frac{n}{N}\right)^\alpha,$$

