- For patient-reported acute toxicity, function, distress and QOL instruments, we will graph and summarize the distributions of scores for each instrument over time noting how many patients have data at each time point. We will analyze the changes over time using mixed effects linear models.

- Secondary Endpoint #6: *To evaluate rates of patient-reported late toxicity, function, distress and QOL every 6 months for 24 months.*
 - PRO-CTCAE, EQ-5D, EORTC QLQ-C30, treatment-related stress questionnaire, perceived stress scale, female sexual function index, and international index of erectile function questionnaire will be collected every 6 months following treatment until 24 months post-treatment.
 - For patient-reported acute toxicity, function, distress and QOL instruments, we will graph and summarize the distributions of scores for each instrument over time noting how many patients have data at each time point. We will analyze the changes over time using mixed effects linear models.

- Secondary Endpoint #7: *To evaluate the value of proton therapy by comparing Time-Driven Activity-Based Costing data from the date of consultation until the date of the 12-week follow up visit post-treatment with contemporary controls treated with VMAT.*
 - TDABC data will be collected for the entire acute episode of care from the date of consultation until the 12-week follow up post-treatment for all patients using previously generated departmental process maps. Costs will be tabulated as either treatment or toxicity-management related.

We will then compare these TDABC data with contemporary controls treated with VMAT (as described above) treated during the same fiscal year.

7.4.3 Exploratory Endpoints:

- Exploratory Endpoint #1: *To compare dose to the pelvic bone marrow, bowel, bladder and genitalia between LET-optimized IMPT, traditionally optimized IMPT and VMAT.*
 - Dosimetric studies will be performed comparing the doses from plans generated using the techniques described above.

- We will record dosimetric differences between conventionally optimized (RBE = 1.1) IMPT plans and LET-optimized IMPT plans for analysis using the Wilcoxon rank-sum test. We will also record how often the LET-optimized IMPT plan is chosen by the treating physician over the conventionally optimized (RBE = 1.1) IMPT plan.

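### Section 6.4.1 has rules for leaving the trial but none for staying in follow-up after stopping treatment, so 12-week data may be lost for reasons related to tolerance

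*Combined protocol and SAP*

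**What the plan says.** Section 6.4.1 of the combined protocol and SAP gives two kinds of exit, both from the trial as a whole. The first is discretionary: a subject may "be dropped from the trial at the discretion of the investigator should any untoward effect occur". The second is mandatory: "A subject must be discontinued from the trial for any of the following reasons", and the list includes "Noncompliance with trial treatment or procedure requirements". The section then provides for replacement: "Additional subjects may be enrolled on an as-needed basis to substitute for patient's removed prior to the first follow up visit after chemoradiation".

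The statistical section counts patients differently. Section 7.3 reads: "To be evaluable for toxicity, patients must have at least one weekly assessments of adverse events (CTCAEv4". Section 7.4.1 has toxicity documented "At baseline, weekly during treatment, and at the 12 week post-treatment follow up appointment", and the comparison with VMAT controls is made "For each cumulative physician-reported toxicity (hematologic, gastrointestinal, genitourinary, dermatologic and other) at 12-weeks post-treatment". For the patient-reported outcomes, section 7.4.2 says: "We will analyze the changes over time using mixed effects linear models". Section 7 gives no missing-data rule beyond reporting how many patients have data at each time point.

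**The concern.** Stopping treatment and leaving the study are different events, and the plan has words only for the second. A patient who declines the remaining fractions or chemotherapy because of side effects can be read as noncompliant with trial treatment, and then has to be discontinued from the trial. Section 3.2.1 itself names hematologic, gastrointestinal and dermatologic toxicity as common causes of treatment interruption, so a trigger for exit lies close to the primary outcome.

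At stake are the cumulative grade 3 or higher toxicity rate, the 12-week complete response rate and the patient-reported outcomes. If they are observed mainly in patients who tolerated IMPT, they will tend to look better than they should. The mixed models do not repair this. They can use scores already recorded, but not toxicity that was never recorded. Through 12 weeks the quality-of-life, stress and sexual-function instruments are scheduled only at baseline and week 12, so a patient removed in between contributes a baseline value alone.

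**Working it through.** **Setting the sections side by side**

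1. *What falls after an early exit.* Section 6.3.8 makes the first follow-up visit, 12±4 weeks after chemoradiation, the only one required on study. Table 1 and sections 6.3.1 to 6.3.7 place CTCAE grading, blood count, examination, endoscopy, CT and all questionnaires there. Weekly assessments not yet done at removal also fall after the exit.
2. *Whether another section brings these data back.* Section 6.4.2 records adverse events during the study and follow-up but does not mention discontinued subjects. Section 6.3.8 queries the records of returning patients for response and survival outcomes, not toxicity or questionnaires. Section 6.2.4 does cover cost data for every enrolled patient.
3. *How a removed patient is counted.* Under 7.3, one on-treatment CTCAE grading makes the patient evaluable. Under 6.4.1, the same patient may be substituted if removed before the 12-week visit. Nothing says whether a substituted patient stays in the toxicity analysis.

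**Reading A: the removed patient stays in and counts as event-free**

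Input: 40 evaluable patients (section 7.2). Let m be the number removed before a first grade 3 or higher event who would have had one by week 12. The documents give no value for m.

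- Fall in the observed rate = m/40. For m = 1 this is 1/40 = 2.5 points; for m = 2, 5 points; for m = 4, 10 points.
- In the McNemar comparison, let b be the pairs with an event in the IMPT patient only, and c those with an event in the control only. Each such patient either lowers b by 1 (control event-free) or raises c by 1 (control had the event). Either way b − c falls by 1, which is again 2.5 points on the paired difference.

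**Reading B: the removed patient is replaced and left out**

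If the replacement has event probability p, leaving out a patient who had or would have had an event lowers the expected rate by (1 − p)/40. Leaving out a patient without an event raises it by p/40. Using the RTOG 0529 rates cited in section 7.4.1 only as illustrative values of p:

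- p = 0.58 (hematologic): fall of 0.42/40 = 1.05 points.
- p = 0.21 (GU/GI): fall of 0.79/40 = 1.98 points.

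The net bias is downward only if removed patients have more toxicity than average.

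**The plan's own figures**

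The enrollment figure follows: 40/(1 − 8/48) = 48. An exact binomial recursion through the Table 3 boundaries reproduces Table 4. At a true grade 4 or higher rate of 0.5 it gives 72.34% early stopping, 7.38% claimed acceptable and mean sample size 26.7 (stated: 72.70%, 7.31%, 26.7). At 0.3 it gives 87.50% claimed acceptable (stated: 87.57%). None of these figures is in dispute.

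They do depend on who is counted. Suppose, as a pure what-if, that 8 of 48 leave uncounted and are replaced, and that a share s of the 8 had the event. At a true rate of 0.5 the rate among those counted is (0.5 − s × 8/48)/(40/48):

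- s = 50%: rate 0.500, chance of claiming acceptable 7.4%
- s = 62.5%: rate 0.475, 12.9%
- s = 75%: rate 0.450, 20.7%
- s = 100%: rate 0.400, 42.8%

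The design limit is 10%. This applies only under Reading B and only to the grade 4 monitoring rule. The number 8 is borrowed for scale and is not a forecast.

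**The case against.** Much of the case on the other side stands.

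- A reader might infer that data collection ends at discontinuation. The plan does not say so; it is silent. Removal for an untoward effect is also discretionary. The loss is permitted, not certain.
- Weekly grading is kept up to removal, and the primary endpoint is cumulative. A patient who stops because of an event already graded 3 or higher counts under 7.3. Only later first events are exposed, and patients removed for toxicity are the least likely to have a later first event.
- A reader might add cost and blood counts to the losses. Section 6.2.4 collects cost data for all enrolled patients. The planned blood-count analyses (sections 6.5.2 and 7.4.3) use nadirs, which rest mainly on the weekly counts.
- The three-month examination, CT and endoscopy are standard of care (Table 2), so they may take place whatever the trial status.
- A reader might infer that VMAT controls keep their toxicity after stopping while IMPT patients do not. Control data come from a separate protocol that is not part of these documents, so this cannot be established.
- A reader might take the 8 of 48 non-evaluable patients as the size of the problem. Under 7.3, not evaluable for toxicity means having no on-treatment grading at all, which is a different group from those removed later for poor tolerance.

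What remains is that nothing directs staff to keep observing a patient who stops treatment, one exit rule is mandatory, and the counting of such a patient is undefined.

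**Conclusion.** The point holds as a gap in the rules, not as a demonstrated bias. Section 6.4.1 merges stopping treatment with leaving the trial, and applying it as written allows 12-week CTCAE, response and patient-reported data, and later on-treatment assessments, to be lost for reasons linked to tolerance. Sections 6.4.1 and 7.3 also leave open whether a patient removed before a first grade 3 or higher event is counted as event-free or replaced and left out.

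The size is unknown because the documents give no removal rate. The only firm statement is per patient: 2.5 points among 40 under Reading A, if that patient would have had an event. A total of 5 or 10 points would need 2 or 4 such patients, and nothing in the plan supports either number. The operating-characteristic range is likewise conditional and should not be quoted as an expected inflation of the safety error rate.

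**What to change.** Leave the listed reasons in 6.4.1 unchanged and add the following:

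- Stopping study treatment does not by itself end follow-up.
- Unless consent to follow-up is withdrawn, the patient is lost, or illness prevents monitoring, the remaining CTCAE, laboratory, response and questionnaire data through 12 weeks are still collected. They come from standard-of-care assessments as clinically appropriate, timed from the last fraction received.
- The date of and reason for stopping radiation and chemotherapy are each recorded.

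Reconcile 6.4.1 with 7.3 so that a patient evaluable under 7.3 stays in the toxicity analysis and is not replaced out of it.

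The cost is a minor amendment and a few extra visits or chart reviews for patients who stop early. Table 1 already lists its assessments as standard of care.
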